## 8.7.5. Vital Signs, Physical Findings, and Other Observations Related to Safety

The following parameters of vital signs will be summarized through descriptive statistics by dose cohort at baseline (defined as the last observation prior to the 1st dose), at each posttreatment time point (defined as the day of dose injection but prior to study drug administration), and at the end of study: body temperature, respiration rate, pulse, blood pressure (diastolic and systolic), and weight. Changes from baseline will be summarized in the same manner

Note that height will be converted to centimeter (cm), weight will be converted to kilogram (kg), and temperature will be converted to Celsius (C).

#### 8.7.6. ECOG Performance Status

A summary of ECOG performance status over time will be presented through the end of the Maintenance Phase, at the end of treatment and for the maximum and minimum across all on-treatment data. The number and percentage of each level will be generated at each planned visit. In addition, a summary of the minimum and maximum status observed during the study will be included.

#### 8.7.7. Concomitant Medications

Other than the study drug, any medication taken by patients during the course of the study with a start date or an end date on or after the first dose of the study drug, or marked as ongoing, will be considered concomitant. Medications stopped prior to the date of the first dose of study drug will not be considered concomitant. The number and percent of patients using each concomitant medication will be summarized according to the World Health Organization (WHO) Drug Dictionary preferred name. Patients with multiple uses of a concomitant medication during a treatment period will be counted once for a given preferred name for the treatment period. Additionally, prior and concomitant medication data will be listed.

Prior and concomitant corticosteroid use will be listed. Corticosteroids will be identified by an answer of "Yes" to the CRF question "Is medication a corticosteroid?".

## 10. Appendix 1 Laboratory Standard Units

Laboratory Test	SI Unit
Albumin	g/L
Alkaline Phosphatase	U/L
Bands	$10^{9}/L$
Basophils	$10^{9}/L$
Bicarbonate	mmol/L
Bilirubin (Direct, Indirect, Total)	μmol/L
Blood Urea Nitrogen	mmol/L
Calcium	mmol/L
Chloride	mmol/L
Creatinine	μmol/L
Eosinophils	$10^9/L$
Glucose	mmol/L
Hematocrit	frac of 1
Hemoglobin	g/L
Lactate Dehydrogenase	U/L
Lymphocytes	$10^{9}/L$
Atypical Lymphocytes	$10^{9}/L$
Magnesium	mmol/L
Mean Corpuscular Hemoglobin	pg
Mean Corpuscular Hemoglobin Conc	g/L
Mean Corpuscular Volume	$\operatorname{fL}$
Monocytes	$10^{9}/L$
Myeloblasts	$10^{9}/L$
Nucleated RBC	$10^{9}/L$
Segmented Neutrophils	$10^{9}/L$
Total Neutrophils	$10^{9}/L$
Phosphorous	mmol/L
Platelets	$10^{9}/L$
Potassium	mmol/L
Total Protein	g/L
Prothrombin Time	S
Partial Thromboplastin Time	S
Red Blood Cells	$10^{12}/L$
Sodium	mmol/L
Aspartate Transaminase	U/L
Alanine Transaminase	U/L
Sodium	mmol/L

Uric Acid	umol/L
White Blood Cells	$10^{9}/L$

## 11. Appendix 2 CTCAE v4.0 grading for laboratory values and QTc

CTCAE v4.0 SOC	CTCAE v4.0 Term	Grade 1	Grade 2	Grade 3	Grade 4
Investigations	White blood cell decreased	$<$ LLN - 3000/mm³; $<$ LLN - 3.0 × $10^9$ /L	<3000 - 2000/mm  ; <3.0 - 2.0 × 10  /L	$<2000$ - $1000/\text{mm}^3$ ; $<2.0$ - $1.0$ × $10^9$ /L	<1000/mm  ; <1.0 × 10  /L
Investigations	Hemoglobin increased	>0 - 2 gm/dL above ULN or above baseline, if baseline is above ULN	>2 - 4 gm/dL above ULN or above baseline, if baseline is above ULN	>4 gm/dL above ULN or above baseline, if baseline is above ULN	-
Blood and lymphatic system disorders	Anemia	Hemoglobin (Hgb) <lln - 10.0 g/dL; <lln -="" 6.2
mmol/L; <lln -="" 100
g/L</lln></lln></lln 	Hgb <10.0 - 8.0 g/dL; <6.2 - 4.9 mmol/L; <100 - 80g/L	Hgb <8.0 g/dL; <4.9 mmol/L; <80 g/L; transfusion indicated	Life- threatening consequences ; urgent intervention indicated
Investigations	Lymphocyte count decreased	<lln -
800/mm^3; <lln -="" 0.8
x10^9 /L</lln></lln>	<800 - 500/mm  ; <0.8 - 0.5 × 10  /L	<500 - 200/mm  ; <0.5 - 0.2 × 10  /L	<200/mm  ; <0.2 × 10  /L
Investigations	Neutrophil count decreased	<lln -
1500/mm^3; <lln -="" 1.5="" ×
10^9/L</lln></lln>	<1500 - 1000/mm  ; <1.5 - 1.0 × 10  /L	<1000 - 500/mm  ; <1.0 - 0.5 × 10  /L	$<500/\text{mm}^3$ ; $<0.5 \times 10^9/\text{L}$
Investigations	Platelet count decreased	<lln -
75,000/mm^3; <lln -="" 75.0
× 10^9/L</lln></lln>	<75,000 - 50,000/mm  ; <75.0 - 50.0 × 10  /L	<50,000 - 25,000/mm  ; <50.0 - 25.0 × 10  /L	<25,000/mm  ; <25.0 × 10  /L
Metabolism and nutrition disorders	Hypoalbumin emia	<lln -="" 3
g/dL; <lln -
30 g/L</lln></lln>	<3 - 2 g/dL; <30 - 20 g/L	<2 g/dL; <20 g/L	Life- threatening consequences ; urgent intervention indicated

CTCAE v4.0 SOC	CTCAE v4.0 Term	Grade 1	Grade 2	Grade 3	Grade 4
Investigations	Alkaline phosphatase increased	>ULN - 2.5 × ULN	>2.5 - 5.0 × ULN	>5.0 - 20.0 × ULN	>20.0 × ULN
Investigations	Alanine aminotransfer ase increased	>ULN - 3.0 × ULN	Asymptomatic with ALT >3.0 - 5.0 × ULN; >3 × ULN with the appearance of worsening of fatigue, nausea, vomiting, right upper quadrant pain or tenderness, fever, rash, or eosinophilia		>20.0 × ULN
Investigations	Aspartate aminotransfer ase increased	>ULN - 3.0 × ULN	Asymptomatic with AST >3.0 - 5.0 × ULN; >3 × ULN with the appearance of worsening of fatigue, nausea, vomiting, right upper quadrant pain or tenderness, fever, rash, or eosinophilia	>5.0 - 20.0 × ULN; >5 × ULN for >2 wks	>20.0 × ULN

CTCAE v4.0 SOC	CTCAE v4.0 Term	Grade 1	Grade 2	Grade 3	Grade 4
Investigations	Blood bilirubin (total) increased	>ULN - 1.5 × ULN	>1.5 - 3.0 × ULN	>3.0 - 10.0 × ULN	>10.0 × ULN
Metabolism and nutrition disorders	Hypercalcemi a	>ULN - 11.5 mg/dL; >ULN - 2.9 mmol/L; Ionized calcium >ULN - 1.5 mmol/L	>11.5 - 12.5 mg/dL; >2.9 - 3.1 mmol/L; Ionized calcium >1.5 - 1.6 mmol/L; symptomatic	>12.5 - 13.5 mg/dL; >3.1 - 3.4 mmol/L; Ionized calcium >1.6 - 1.8 mmol/L; hospitalizatio n indicated	>13.5 mg/dL; >3.4 mmol/L; Ionized calcium >1.8 mmol/L; life-threateni ng consequences
Metabolism and nutrition disorders	Hypocalcemi a	<lln -="" 8.0
mg/dL; <lln -="" 2.0
mmol/L; Ionized calcium <lln -="" 1.0
mmol/L</lln></lln></lln>	<8.0 - 7.0 mg/dL; <2.0 - 1.75 mmol/L; Ionized calcium <1.0 - 0.9 mmol/L; symptomatic	<7.0 - 6.0 mg/dL; <1.75 - 1.5 mmol/L; Ionized calcium <0.9 - 0.8 mmol/L; hospitalizatio n indicated	<6.0 mg/dL; <1.5 mmol/L; Ionized calcium <0.8 mmol/L; life threatenin g consequences
Investigations	Creatinine increased	>1 - 1.5 × baseline; >ULN - 1.5 × ULN	>1.5 - 3.0 × baseline; >1.5 - 3.0 × ULN	>3.0 baseline; >3.0 - 6.0 × ULN	>6.0 × ULN

CTCAE v4.0 SOC	CTCAE v4.0 Term	Grade 1	Grade 2	Grade 3	Grade 4
Metabolism and nutrition disorders	Hyperglycem ia	Fasting glucose value >ULN - 160 mg/dL; Fasting glucose value >ULN - 8.9 mmol/L	Fasting glucose value >160 - 250 mg/dL; Fasting glucose value >8.9 - 13.9 mmol/L	>250 - 500 mg/dL; >13.9 - 27.8 mmol/L; hospitalizatio n indicated	>500 mg/dL; >27.8 mmol/L; life-threateni ng consequences
Metabolism and nutrition disorders	Hypoglycemi a	<lln -="" 55
mg/dL; <lln -="" 3.0
mmol/L</lln></lln>	<55 - 40 mg/dL; <3.0 - 2.2 mmol/L	<40 - 30 mg/dL; <2.2 - 1.7 mmol/L	<30 mg/dL; <1.7 mmol/L; life-threateni ng consequences ; seizures
Metabolism and nutrition disorders	Hypermagnes emia	>ULN - 3.0 mg/dL; >ULN - 1.23 mmol/L	-	>3.0 - 8.0 mg/dL; >1.23 - 3.30 mmol/L	>8.0 mg/dL; >3.30 mmol/L; life-threateni ng consequences
Metabolism and nutrition disorders	Hypomagnes emia	<lln -="" 1.2
mg/dL; <lln -="" 0.5
mmol/L</lln></lln>	<1.2 - 0.9 mg/dL; <0.5 - 0.4 mmol/L	<0.9 - 0.7 mg/dL; <0.4 - 0.3 mmol/L	<0.7 mg/dL; <0.3 mmol/L; life-threateni ng consequences
Metabolism and nutrition disorders	Hypophospha temia	<lln -="" 2.5
mg/dL; <lln -="" 0.8
mmol/L</lln></lln>	<2.5 - 2.0 mg/dL; <0.8 - 0.6 mmol/L	<2.0 - 1.0 mg/dL; <0.6 - 0.3 mmol/L	<1.0 mg/dL; <0.3 mmol/L; life-threateni ng consequences
Metabolism and nutrition disorders	Hyperkalemia	>ULN - 5.5 mmol/L	>5.5 - 6.0 mmol/L	>6.0 - 7.0 mmol/L; hospitalizatio n indicated	>7.0 mmol/L; life-threateni ng consequences

CTCAE v4.0 SOC	CTCAE v4.0 Term	Grade 1	Grade 2	Grade 3	Grade 4
Metabolism and nutrition disorders	Hypokalemia	<lln -="" 3.0
mmol/L</lln>	<lln -="" 3.0
mmol/L; symptomatic; intervention indicated</lln>	<3.0 - 2.5 mmol/L; hospitalizatio n indicated	<2.5 mmol/L; life-threateni ng consequences
Metabolism and nutrition disorders	Hyponatremi a	<lln -="" 130
mmol/L</lln>	-	<130 - 120 mmol/L	<120 mmol/L; life-threateni ng consequences
Metabolism and nutrition disorders	Hypernatremi a	>ULN - 150 mmol/L	>150 - 155 mmol/L	>155 - 160 mmol/L; hospitalizatio n indicated	>160 mmol/L; life- threatening consequences
Electrocardio gram QT corrected interval prolonged		QTc 450 - 480 ms	QTc 481 - 500 ms	QTc >= 501 ms	

Note: Laboratory measurements that are within their institutional limits of normal and are not graded as 1-4, per the CTCAE, will be summarized as "Grade 0", which is defined as normal.

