## 8.7.3.5. CTCAE Coding of Laboratory Data

Where laboratory values are categorized into NCI CTCAE version 4.0 grades, the categories are defined according to the criteria available on the following website:

http://evs.nci.nih.gov/ftp1/CTCAE/About.html

Note that grades are applied based only on the numeric value of the parameter assessed; clinical signs and symptoms are not considered. For example, Grade 4 hyperglycemia will be assigned based solely on the value of the glucose measurement, and acidosis will not be considered. Where categories are only distinguished by clinical signs or symptoms, the lowest of the possible grades will be assigned that do not involve the clinical sign or symptom described. Grade 0 means normal.

NCI CTCAE grades will be applied for the following lab parameters (given in Appendix 2):

- Hematology: hemoglobin (anemia, hemoglobin increased), total WBC (leukopenia), lymphocytes (lymphopenia), neutrophils (neutropenia), and platelets (thrombocytopenia).
- Chemistry: albumin (hypoalbuminemia), alkaline phosphatase, ALT, AST, total bilirubin, calcium (hypocalcemia, hypercalcemia), creatinine, glucose (hyperglycemia, hypoglycemia), magnesium (hypermagnesemia, hypomagnesemia), phosphorus (hypophosphatemia), potassium (hyperkalemia, hypokalemia), and sodium (hyponatremia, hypernatremia).

A summary of maximum severity observed on-study for all parameters noted above will be generated for the coded hematology and chemistry parameters. Patients will only be included once, in the maximum severity, for each laboratory parameter. Additionally, a shift summary of baseline to maximum severity on-study will also be produced. Patients with at least 1 on-study measurement for each laboratory parameter will be included, regardless of whether or not a baseline assessment is present (baseline will be included as a missing category). Thus, percentages for each parameter will be based on the total number of patients with an on-study measurement for the parameter of interest.

Laboratory measurements that are within their institutional limits of normal and are not graded as 1-4, per the CTCAE, will be summarized as "Grade 0," which is defined as normal.

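### Two laboratory grading rules make the creatinine Grade 1 counts largely noise and leave values abnormal in an ungraded direction with no category

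*SAP*

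**What the plan says.** **Creatinine.** In SAP Appendix 2, creatinine is Grade 1 at ">1 - 1.5 × baseline; >ULN - 1.5 × ULN" and Grade 2 at ">1.5 - 3.0 × baseline; >1.5 - 3.0 × ULN". The baseline part of Grade 1 has no minimum rise and does not require the value to exceed ULN. The only other row in that appendix that refers to baseline, hemoglobin increased, does so only where the baseline itself is above ULN.

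**How grades are assigned.** SAP 8.7.3.5 states that "grades are applied based only on the numeric value of the parameter assessed; clinical signs and symptoms are not considered". Section 8 generally takes baseline as one value, the last non-missing one before first dose.

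**Grade 0.** Section 8.7.3.5 says "Grade 0 means normal" and later: "Laboratory measurements that are within their institutional limits of normal and are not graded as 1-4, per the CTCAE, will be summarized as" Grade 0. The note under Appendix 2 repeats the second sentence. A value must therefore meet two conditions: inside normal limits, and not graded 1-4.

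**Tables.** "A summary of maximum severity observed on-study for all parameters noted above will be generated", with each patient counted once per parameter, and "a shift summary of baseline to maximum severity on-study will also be produced". The denominator is every patient with an on-study value for the parameter. A missing category is provided for patients who have no baseline assessment.

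**Directions graded.** WBC, lymphocytes, neutrophils and platelets are graded for low values only. Several chemistry parameters are also graded in one direction only.

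**The concern.** Laboratory findings are part of the primary safety endpoint (SAP 6.2), and these two tables condense them by grade.

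(a) A single baseline is compared with the worst of many later values, and any excess counts. Chance variation alone then moves patients from Grade 0 to Grade 1. A baseline cannot exceed itself, so the baseline part of the rule acts only after baseline and only upward. The Grade 0 sentence does not help, because it excludes values that already carry a grade.

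(b) A value outside normal limits on a side that is not graded meets neither the Grade 0 definition nor any of Grades 1-4. If it is the baseline, the patient has no defined row in the shift table but still counts in the denominator. The rows then need not sum to 100%, and the programmer has to invent a category. AML patients enter Part 2 without hematology eligibility limits (Amendment No. 6 summary), so baseline counts are not constrained there.

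**Working it through.** The documents give no rate on this point, so there is no planned figure to reproduce.

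**(a) Creatinine**

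*The rule on examples* (ULN of 105 µmol/L assumed):

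| Baseline | Later value | Ratio | Grade at baseline, then later |
|---|---|---|---|
| 70 | 69 | 0.99 | 0, then 0 |
| 70 | 71 | 1.01 | 0, then 1 |
| 60 | 91 | 1.52 | 0, then 2 (still below ULN) |
| 110 | 112 | 1.02 | 1, then 1 |

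*Number of draws* (SAP Tables 1-4, assuming creatinine is in every chemistry panel; the protocol appendix listing the tests is not available):
- Part 1: Days 8, 15, 22, 29, 43, 57, 71 and 85 give k = 8; with End of Study, k = 9.
- Part 2: eight induction visits (Days 8 to 57) and six consolidation visits (Days 71 to 141) give k = 14; with End of Study, k = 15. Some Table 4 cells are broken, so this count assumes a draw at each dosing visit.

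*Probability with no drug effect.* If a patient's baseline and k later values are exchangeable and continuous, each of the k + 1 is equally likely to be the largest. The baseline is largest with probability 1/(k+1), so P(at least Grade 1) is at least k/(k+1). This holds whatever the within-patient SD.

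| k | k/(k+1) |
|---|---|
| 1 | 50.0% |
| 4 | 80.0% |
| 8 | 88.9% |
| 9 | 90.0% |
| 14 | 93.3% |
| 15 | 93.8% |

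For a 10-patient cohort at k = 9, the expected number flagged is 10 × 0.9 = 9. P(at least 8 of 10) = 0.194 + 0.387 + 0.349 = 0.93.

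*Rounding.* Ties with baseline lower the rate. Two no-effect simulations, with all inputs assumed:
- True mean 75 µmol/L (SD 12), ULN 105, within-patient CV 3% to 12%, baseline not above ULN, k = 9. Reported to 1 µmol/L: 86% to 90%. Reported to 0.1 mg/dL: 39% to 81%. Counting only values above ULN, with 1 µmol/L reporting: 0.6% to 11.4%.
- True value uniform on 0.6-1.1 mg/dL, within-patient SD 0.04 to 0.10 mg/dL, reported to 0.1 mg/dL. 8 draws: about 55% to 78%. 14 draws: about 63% to 85%.

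**(b) Ungraded direction**

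The 17 graded parameters in 8.7.3.5 divide as follows:
- Both directions (6): hemoglobin, calcium, glucose, magnesium, potassium, sodium.
- Low only (6): WBC, lymphocytes, neutrophils, platelets, albumin, phosphorus.
- High only (5): ALP, ALT, AST, total bilirubin, creatinine.

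So 6 + 5 = 11 of 17 have an ungraded side. Take a baseline WBC above ULN. It is not within limits, so it is not Grade 0. The Appendix 2 WBC grades all lie below LLN, so it is not Grade 1-4. A baseline assessment exists, so the missing category does not describe it. No row is left.

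If a share q of baselines lies on the ungraded side, q of patients lack a shift-table row. In the maximum-severity table a patient drops out only if every on-study value lies there. That share runs from q^k (independent visits) to q (a persistent abnormality). For an assumed q of 0.30 and k = 4, the lower end is 0.30^4 = 0.8% and the upper end 30%. The documents give no value for q.

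**The case against.** **The creatinine row is the scale itself.** Appendix 2 presents it as CTCAE v4.0 grading, and a reader might infer a transcription error. The documents show none. The difficulty comes from applying the row by number alone to the worst of many visits. It is therefore wrong to strike out part of a pre-specified scale. Requiring the baseline part also to exceed ULN would simply delete it, since any value above ULN already has a grade. A normal value at 1.49 × baseline would then be Grade 0 and one at 1.51 × baseline Grade 2. This objection stands and shapes the fix.

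**A real renal signal would still be seen.** A reader might infer that it would be hidden. Grades 2-4 are unchanged. Creatinine is also summarized by visit with change from baseline, out-of-range values are flagged in listings (8.7.3.2), and maximum and minimum values are tabulated (8.7.3). What is lost is the meaning of the Grade 1 row and of the 0-to-1 shift.

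**The percentages rest on assumptions.** This stands in part. Retention is not given, and the figure is 50% at k = 1. With coarse rounding and small variation, fewer than half of patients may be flagged. Even 39% with no drug effect makes the row hard to interpret.

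**The gap in (b) is narrow.** A reader might infer that AML patients disappear from the hematology tables. They do not: a fall to Grade 3 leukopenia still counts as the on-study maximum, and only the baseline label is undefined. High glucose is not an example if tables are per parameter, as 8.7.3.5 words it; it becomes one only if they are run per CTCAE term. Nor do the documents say how often high counts occur in AML; they mention expected cytopenias.

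**Conclusion.** Both points hold as defects of the descriptive laboratory tables.

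(a) Any post-baseline creatinine above the patient's own baseline is at least Grade 1, even within the normal range. Under no drug effect and exchangeable values this flags 88.9% of patients with 8 draws and 93.3% with 14, given creatinine in every panel and continued participation. Rounding to 0.1 mg/dL brings it to roughly 39-85% for 8 to 14 draws under the assumed variation. Grade 1 and the 0-to-1 shift are largely noise; larger rises remain visible.

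(b) For 11 of 17 parameters, a value abnormal on the ungraded side has no category. This mainly affects the baseline rows of the shift table. Its frequency cannot be derived from the documents.

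A reader might connect this to dose escalation, because the DLT definition uses a 2-grade hematology shift. The documents do not support that: DLTs are flagged in the adverse event data (8.7.1), not taken from these tables. The DLT and MTD decisions are unaffected.

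**What to change.** (a) Keep the CTCAE v4.0 creatinine grading as pre-specified. Add to 8.7.3.5 a second creatinine display, or a footnoted split of Grade 1, that counts Grade 1 only when the value exceeds ULN. Cost: one extra row or table.

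(b) Either define Grade 0 as not meeting Grade 1-4 for that parameter or term, or add a row for values outside normal limits in the ungraded direction. The first option means revising both Grade 0 statements in 8.7.3.5 and the note under Appendix 2, because a high WBC would then be Grade 0 without being normal. The second keeps Grade 0 as normal and adds one row. Either way, state whether the tables are per parameter or per CTCAE term, and check that the categories sum to the stated denominator. Cost: a few lines of SAP text and programming, with no new data.
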